1 INTRODUCTION

Achilles tendinopathy is a frequent and often long-term injury especially seen in sports active. The cumulative incidence in former elite athletes is 50% compared to 5.9% in inactive athletes (Kujala, 2005). In particular, athletes involved in running and jumping are at risk (Kvist 1991). In the case of runners, the incidence is 9% (Lysholm 1987).

As primary treatment, eccentric exercises are recommended, where load reduction is described in 60% to 90% of patients (Silbernagel 2001, Maffuli 2008, Ohberg 2004). Other studies have shown the effect of stretching exercises (Porter 2002), and in a randomized study, no difference in outcomes could be detected when treated with eccentric exercises compared to stretching exercises (Nørregård 2007). In a recent study at our institute, slow heavy strength training 3 times a week has been shown to have the same treatment effect as daily eccentric training (Beyer 2015). In these randomized efficacy studies in exercise-motivated patients, an improvement is seen in 60-90%. However, in a pragmatic effectiveness study, we found that only 26% performed satisfactorily with training alone (Wetke 2015), and in a Canadian study, only 10% had satisfactory effects of eccentric home training (Ram 2013). This is consistent with the clinical experience, where we find that a significant proportion of exercisers do not improve significantly by training alone.

Corticosteroid injection (CS) is often used in the clinic, but since there is rarely evidence of inflammation in the Achilles tendons, the rationale behind the treatment is controversial (Khan 2002). However, a randomized clinical controlled trial (RCT) has shown good efficacy of CS injections given ultrasound-guided to patients with chronic achilles tendinopathy (Fredberg 2004). A significant short-term effect on symptoms and thickness of the tendons was observed, but with relapses after 6 months, possibly due to an aggressive rehabilitation course. In the study by Wetke (2015), it was found that patients who did not improve from exercise therapy alone, had a good effect by supplementing the training with injection of CS (40 mg Depomedrol). This resulted in 76% being cured or clearly better. Whether this effect was due to the fact that the 2 ml injected caused a slight rupture of the peritendinous tissue, from which vascular ingrowth into the tendon is frequently seen in Achilles tendinopathy (Johannsen 2010, Sterkenburg 2011) or an anti-inflammatory effect of CS is not known. Boesen (2016) documented that training supplemented by "High Volume Injection" (HVI), in which 50 ml (saline, local anesthesia, CS (20 mg Depomedrol))

US guided into the peritendinous and thus loosens the entire tenosynovium, had better effect than training supplemented with placebo injection and training supplemented with "platelet rich plasma" (PRP) injection. In another study, the same group has shown better effect of HVI with CS than HVI without CS (Boesen in press).

According to clinical guidelines in the Danish Sports Medicine Society (DIMS) and the Danish Rheumatology Society (DRS), the existing standard treatment of AT is primarily load reduction supplemented by training with stimulating exercises. If necessary, this can be supplemented by injection of CS, usually mixed with local anesthetics.

In cases where the above treatment measures are ineffective, surgery may be considered. Surgery of midsection AT has been tried for many years. Traditionally with longitudinal incisions of the tendon in the thickened part, but in recent years mainly as a minor intervention with a removal of the peritendium around the tendon (tenolysis) – especially on the front of the tendon, where vascular ingrowth with nerve fibers is assumed to be a large part of the cause of the pain from the tendon. Ruergård A et al (2019) have indicated a success rate of 89% with painlessness and return to sports at the same level as before the Achilles problems. In addition to this study, there are only small retrospective series of the effect of tenolysis, and in all the studies it is unclear to what extent and how effectively conservative treatment has been tried.

The purpose of our study is to compare an app based daily home training with physiotherapist supervised slow heavy strength training combined with load reduction by abstaining from running and jumping activities. This will be interesting because app based training is less costly than physiotherapeutic guided training. In addition, we will compare 50 ml of HVI with CS with 2 ml of CS injection as a supplement to training, in those patients who do not achieve satisfactory results with training alone. Finally, patients with continued problems will be offered surgery with Achilles tenolysis in an open prospective study.

The study is based on the following hypotheses:

- 1) Treatment with an app based daily home workout is as effective as slow heavy strength training (non-inferiority study).
- 2) 50 ml HVI with CS is better than 2 ml CS injection in addition to continued training, in those patients who do not achieve satisfactory results with training alone (superiority study).

- 3) Surgery with surgical tenolysis results in a clinically relevant reduction of pain symptoms in patients without sufficient effect of structured and monitored conservative treatment (the above conservative regimen).

2 MATERIAL AND METHODS

Patients with suspected Achilles tendinopathy are usually referred to the Department of Sports Medicine, BBH or specialist practice in rheumatology.

Inclusion Criteria:

1. Ultrasound diagnosed mid-substance Achilles tendinopathy.
2. For unilateral symptoms, symptomatic Achilles tendon should be more than 20% thicker than on the asymptomatic side or more than 7 mm thick
3. For bilateral symptoms, the Achilles tendon should have a diameter above 7 mm.
4. Duration of pain should be a minimum of 3 months
5. Participants are at least 18 years old and a maximum of 65 years old.
6. Participant may provide relevant and adequate informed consent.
7. The patient must have a smartphone that can work with the training app: Injurymap.

Exclusion criteria:

1. Previous lower limb surgery. Arthroscopy of the knee excepted.
2. No known medical conditions, including insulin-dependent diabetes mellitus or rheumatic diseases.
3. Infection of the foot or lower leg.
4. Mental state that does not allow participation.
5. Judged not to be able to follow the exercise intervention.
6. Lack of presence in the region during the project period.
7. Daily use of painkillers.
8. Cannot read or understand Danish*.
9. Corticosteroid injection to treat Achilles tendinopathy within the last 6 months.
10. Previous allergic reaction to treatment with corticosteroid (Depomedrol®) or local anesthetics.

11. Pregnancy/breastfeeding or planning of pregnancy during the intervention period.

*Due to the cost of an interpreter and home training app in Danish, the subjects need to be able to read and understand Danish.

3 STUDY METHODS

Sub-study 1:

Single blinded (assessor and statistics) Randomized Controlled Trial.

Randomization method

Randomization must be preceded by informed consent and power of attorney. The randomization of patients is performed by an independent office employee not involved in patient care ([name]) using a computer generated randomization schedule (MINIMPY, Maghaei 2010) using permuted block sizes (four to six). The employee is blinded to the block sizes. The allocation of each patient is stored in a computer drive with exclusive access only for the responsible office employee ([name]). Patients will be divided equally into 2 groups. Symptom duration will be stratified < 1 year> and VISA-A score (0-100) at entry <50>

The secretary is then in charge of filling out randomization sheets and preparing the CRF (clinical research files).

Blinding

The study will be evaluated blinded. Patients cannot be blinded to the training performed. The effect of the training is evaluated monthly by the patient himself at home without interference with any investigators on an app (Redcap). At every doctors appointment US assessment of the Achilles tendon will be performed.

The 2 primary treatment arms are:

	Statistical Analysis Plan	Date: nov 27, 2022
	Exercise/Injections/operation in Achilles midsubstance tendinopathy	
Bispebjerg Hospital		

GROUP 1 (HSR): Treatment with **Heavy Slow Resistance training** (HSR) thoroughly guided by physiotherapists. The training will take place in a gym and lasts for 3 months. Simultaneous load reduction from harmful activities (running, jumping) is advocated.

GROUP 2 (App): Treatment with 3 months of **home training guided via an app (Injurymap)**. The only aid is a rubber band. Simultaneous load reduction from harmful activities (running, jumping) is advocated.

Description of the load reduction during the controlled training

The first 3 months the patients is advocated to abstain from all jumping and running activities (impact training). They are free to do non-impact training such as cycling, swimming, rowing and strength training. After 3 months of controlled rehabilitation, patients should slowly return to their previous sports activity and level, without provoking further pain or morning stiffness.

Description of Heavy Slow Resistance Exercise

The strength training will consist of a gradual progressive training program with training 3 times a week starting after instruction by the physiotherapist. The training is supervised by a physiotherapist for the first 3 months by supervised training 4 times or more if needed. As the tissue becomes stronger and the pain becomes less, the tissue is challenged at higher loads. Instruction in the exercises will be handled by two project physiotherapists. The exercises are also handed out in text and images. For bilateral symptoms, both sides must be trained, but only one side is included in the evaluation of effect parameters. For unilateral symptoms, only the symptomatic side is trained

Description of app guided home workouts

The app contains the same exercises that were included in the study of Wetke (2015). The exercises do not require special equipment and can be performed at home at convenient times. The exercises only use the patient's own body weight or an exercise rubber band as a load. The exercises include movement exercises, balance exercises, strength exercises and stretching exercises. The strength exercises start without dorsal flexion in the ankle and are slowly progressed with increasing dorsal flexion if this does not trigger pain of 50 or more on a VAS 100 pain score. The app contains an algorithm that responds to the patient's feedback on each exercise (difficulty of the exercise, pain provocation of the exercise) and based on this, the app assesses which exercises to offer next time.

It is thus an interactive app that results in an individual training program, as the exercises are

	Statistical Analysis Plan	Date: nov 27, 2022
Bispebjerg Hospital	Exercise/Injections/operation in Achilles midsubstance tendinopathy	

offered in different order and with different progression depending on the patient's feedback. See www.injurymap.com/da/doctors/diagnoses under "Achilles tendonitis".

Trial Design

Substudy 1 is an evaluator blinded randomized controlled trial with follow-up after 3, 6, 9 and 12 months. Patients not satisfied with the outcome in substudy 1 after at least 1 month of training, have the possibility to drop-out of this substudy and be included in substudy 2. Drop-outs are recorded as “non-survivors” and a "Survival" curve is recorded for each exercise group. A total of 90 patients are included, 45 patients in each of the 2 training groups. All patients will be included in the intention to treat analysis, but we will also perform a per-protocol analysis only including patients performing at least 75% of the training programs.

Anyone who ceases due to unsatisfactory effect in sub-study 1 can be included in the second part of the study after at least 1 months of training and no later than after 12 months.

Sub-study 2

Single blinded (assessor and statistics) Randomized Controlled Trial.

Randomization method

Randomization must be preceded by informed consent and power of attorney. The randomization of patients is performed by an independent office employee not involved in patient care ([name]) using a computer generated randomization schedule (MINIMPY, Maghaei 2010) using permuted block sizes (two to four). The employee is blinded to the block sizes. The allocation of each patient is stored in a computer drive with exclusive access only for the responsible office employee ([name]). Patients will be divided equally into 4 groups. No further stratification will be carried out in part 2 of the study.

The secretary is then in charge of filling out randomization sheets and preparing the CRF (clinical research files).

Blinding

The study will be evaluated blinded. The doctors who give the injections cannot be blinded due to the large difference in the injection volume. Patients cannot be blinded to the training performed and can probably feel whether a small or large volume is being injected. The effect of the training is evaluated monthly by the patient himself at home without interference with any investigators on an app (Redcap). At every doctors appointment US assessment of the Achilles tendon will be performed.

The 4 secondary treatment arms

Patients continue in the allocated training (Heavy Slow Resistance exercise or App guided training) and treatment is supplemented with either corticosteroid injection (CS) or High Volume Injection (HVI). This results in 4 groups:

GROUP 3 (HSR+HVI): Continued Heavy Slow Resistance exercise supplemented by injection of 50 ml of HVI with CS (9.5 ml Lidocaine + 20 mg Depomedrol 40 mg/ml, followed by 40 ml isotonic saline). Only one injection is given (Boesen 2017)

GROUP 4 (HSR+CS): Continued Heavy Slow Resistance exercise supplemented by injection of 1 ml Lidocaine + 1 ml (40 mg/ml) corticosteroid (Depomedrol®) , total 2 ml (standard care). Injection is given every 6 weeks if needed. Max 3 injections.

GROUP 5 (app+HVI): Continued app-based training supplemented by injection of 50 ml HVI with CS (9.5 ml Lidocaine + 20 mg Depomedrol 40 mg/ml, followed by 40 ml isotonic saline). Only one injection is given (Boesen 2017)

GROUP 6 (app+CS): Continued app based training supplemented by injection with 1 ml. Lidocaine + 1 ml (40 mg/ml) corticosteroid (Depomedrol®), total 2 ml (standard care). Injection is given every 6 weeks if needed. Max 3 injections.

Description of the load reduction and controlled exercise therapy

Continuous as described under sub-study 1.

Description of injection of 2 ml with corticosteroid

The injection consists of the mixture of the corticosteroid: Depo-medrol[®] 1 ml (40mg/ml) and 1 ml Lidocaine 1%. The mixture will be injected underneath the thickest part of the tendon. Regardless of whether the symptoms are bilateral or unilateral, only one side is selected for treatment. The first corticosteroid injection is given to everyone included in this group. The second corticosteroid injection after 1 month is given only if the tendon is over 7 mm thick or more than 20% thicker than the healthy one. The third injection is given 2 months after inclusion if, in addition to continued thickening, there is also morning pain above VAS 20 (100 mm VAS score) or VAS under function above 20 (100 mm VAS score). Thus, a maximum of 3 corticosteroid injections are given. This is the usual standard treatment.

Description of injection of 50 ml HVI and corticosteroid.

The injection consists of the mixture of the corticosteroid: depo-medrol[®] 0.5 ml (40mg/ml) and 9.5 ml lidocaine 1%. The mixture will be injected underneath the thickest part of the tendon. The needle remains in place and 2 x 20 ml of isotonic saline is injected afterwards. Regardless of whether the symptoms are bilateral or unilateral, only one side is selected for treatment. The injection is made only once.

Trial Design

Substudy 2 is also an evaluator blinded randomized controlled trial with follow up after 1,2,3,6,9,12 months.

Anyone who ceases due to unsatisfactory effect in sub-study 2 can be included in the third part of the study after at least 3 months of exercise therapy and no later than after 12 months.

Sub-study 3:

Open prospective study

Patients who do not achieve sufficient efficacy from conservative treatment in sub-studies 1 and 2 will be offered surgery with tenolysis, which is the standard treatment for patients with Achilles tendonopathy who do not respond adequately to conservative treatment. The operation is performed at the Sports Surgery Section, Orthopaedic Surgery Department, Bispebjerg Hospital.

Description of the operation

The patient is operated on in lower leg block or universal anesthesia.

Preoperative antibiotics with either Dicillin 2 g iv or Zinacef 11/2 g iv.

The thickening of the tendon is determined by palpation. Incision (about 3 cm long) is made corresponding to the anterior/medial edge of the tendon along the thickened part of the tendon. The peritendium is cleaved and the tendon is released from the peritendium throughout the circumference corresponding to the swelling and approximately 3 cm distally and proximally to the swelling. Afterwards the skin is closed with nylon sutures.

Trial Design

Open prospective quality assurance study with follow-up 3, 6 and 12 months after surgery

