In a previous study, 25% achieved satisfactory effect from training alone. If the same is seen in the current study, approximately 67 will want additional treatment. Of these, we expect that 50 will continue in sub-study 2. Sub-study 2 is a superiority study, and 22 patients are needed to have an 80% chance of finding, with 5% significance level, a difference in VISA-A scores of more than 11 between treatment groups using Mixed Effect Analysis using the intention to treat principle. Patients are divided into 4 groups, but this sub study will be powered to detect differences between exercise therapy+HVI and Exercise therapy +CS injection. This means that the combination of group 3 and group 5 are compared to the combination of group 4 and group 6. However, we will also compare group 3 to group 4, and group 5 to group 6.

Q-Q plots will be visually examined to ensure that the assumption of normal distribution is not violated prior to analysis.

Sub-study 3

	Statistical Analysis Plan	Date: nov 27, 2022
Bispebjerg Hospital	Exercise/Injections/operation in Achilles midsubstance tendinopathy	

is a prospective quality assurance study. Paired T-test is used for calculating differences from before operation to 3, 6 and 12 months after operation. Change in VISA-A score is the primary outcome at 6 and 12 months, with an expected preoperative score of 50 and a relevant improvement is set to 15. The standard deviation of the difference is from earlier studies 13. In order to record an improvement of at least 15 points with a risk of type I error of 5% and type II error of 20%, 8 patients would have to be included in this study.

Data processing:

Entry data is registered in Redcap, where all information from each individual subject is collected.

Each patient is assigned an anonymous unidentifiable project number: Ach2019-n.

Project numbers are listed on all CRF and patient diaries.

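### Sub-study 2's equal split into four groups conflicts with the fixed training arm; the SAP should state a 1:1 HVI:CS draw, say whether it is balanced within training arm, and put training arm in the pooled model

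*SAP*

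**What the plan says.** In SAP section 3, Sub-study 2, the Randomization method paragraph describes a computer-generated schedule "using permuted block sizes (two to four") and then states: "Patients will be divided equally into 4 groups. No further stratification will be carried out in part 2 of the study".

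Under The 4 secondary treatment arms, the same section says: "Patients continue in the allocated training (Heavy Slow Resistance exercise or App guided training"). It adds one of the two injections, HVI or CS, and presents the four groups as the result. Groups 3 and 4 are continued HSR with HVI or CS. Groups 5 and 6 are continued app training with HVI or CS.

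Entry is by dissatisfaction with training: "Anyone who ceases due to unsatisfactory effect in sub-study 1 can be included in the second part of the study".

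Section 5, Sub-study 2, expects 50 entrants ("Of these, we expect that 50 will continue in sub-study 2") and gives the powered contrast: "the combination of group 3 and group 5 are compared to the combination of group 4 and group 6". It also plans 3 v 4 and 5 v 6. The only model factors named are treatment group and time, in section 5 under Sub-study 1. Section 7.2 names none for sub-study 2.

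By contrast, the sub-study 1 list has stated strata: "Symptom duration will be stratified < 1 year> and VISA-A score (0-100) at entry <50>".

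**The concern.** A patient who trained with HSR can enter only group 3 or 4, and an app patient only group 5 or 6. A sub-study 2 draw cannot make the four groups equal, because the HSR:app ratio among entrants is set by exits from sub-study 1, which are themselves an outcome there (the survival comparison in section 7.2). The block sizes do not suit four groups either: a block of two or three cannot hold four arms in equal number.

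Once the rule is read as a two-arm injection draw, a second gap appears. The SAP nowhere says that the list is kept by training arm, and the sentence on stratification can be read as excluding it. With one list, HVI and CS are balanced overall but only by chance within each training. If the trainings differ in effect, that imbalance adds noise to the pooled HVI-CS contrast, and no stated model term removes it.

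**Working it through.** **The plan's own figure.** Inputs: difference 11, 80% power and 5% significance (section 5, Sub-study 2); two-sided testing (section 7.2); SD 13 (stated for sub-study 1 and assumed to carry over).

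n per pooled group = 2 × [13 × (1.960 + 0.842) / 11]² = 21.9, so 22.

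This matches the stated 22. The allocation rule does not enter the formula, so the figure is unaffected.

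**The four-group rule taken literally.**
- Two of the four groups belong to the other training, so an equal four-way draw would give half the patients, 25 of 50 on average, a group that does not match their training.
- Four equal groups would need equal exits from both training arms. With exits of 30 and 20 (an illustration), a 1:1 injection draw gives about 15, 15, 10 and 10.
- A block of three fits neither a four-group nor a 1:1 two-group draw. Blocks of 2 and 4 fit the two-group draw.

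**Chance imbalance with one list.** Assume 50 entrants, 25 per training arm, 25 HVI and 25 CS. The number X of HVI patients within one training arm is hypergeometric.

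| Split within a training arm | Exact probability | Simulation, one list, random blocks of 2 or 4 |
|---|---|---|
| 15:10 or worse | 0.258 | 0.262 |
| 16:9 or worse | 0.089 | 0.091 |
| 17:8 or worse | 0.023 | 0.023 |

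In the same simulation (20,000 runs), a separate list per training arm always gave 13:12. With a 30/20 exit split, 18:12 or worse in the larger arm occurred in about 15% of runs with one list and in none with separate lists.

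**Effect on the pooled contrast (3+5 v 4+6).** Assume the trainings differ by 7.5 points, the sub-study 1 margin.
- Shift = 7.5 × (2X − 25)/25. With 15:10 in one arm and 10:15 in the other, this is 7.5 × (15/25 − 10/25) = 1.5 points.
- Var(X) = 25 × 0.5 × 0.5 × 25/49 = 3.19, so SD(X) = 1.79.
- The shift therefore has mean 0 and SD 7.5 × 2 × 1.79/25 = 1.07 points.
- Standard error of the HVI-CS difference = 13 × √(1/25 + 1/25) = 3.68.
- Combined: √(3.68² + 1.07²) = 3.83, an increase of about 4%.

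**Effect on 3 v 4 and 5 v 6.** Normal approximation, difference 11, SD 13; standard error = 13 × √(1/a + 1/b).

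| Split | Standard error | Power |
|---|---|---|
| 13:12 | 5.20 | 56% |
| 15:10 | 5.31 | 54% |
| 16:9 | 5.42 | 53% |
| 17:8 | 5.58 | 51% |

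**The case against.** The strongest reply is that the section explains itself. Patients continue their training, an injection is added, and four groups result. The sample size concerns HVI against CS only, and the Data processing text in section 5 pools the patients into two injection groups. Blocks of two fit a two-arm draw. This stands: a 1:1 injection draw can be carried out and is probably what is meant. A reader might infer that the SAP re-randomises training, or that sub-study 2 cannot be run. The text on continued training excludes the first, and the workable reading disposes of the second.

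The wording on stratification may also mean none beyond training arm. That is possible, and if lists are already kept by training arm the imbalance calculated above disappears. But the SAP does not say so, and a single list is equally consistent with its words.

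A reader might also infer that the pooled comparison is biased, or that all three comparisons are confounded by training. Neither is supported. Injection is still randomised, so the pooled estimate is unbiased by design and the shift averages zero. Comparisons 3 v 4 and 5 v 6 each lie within one training, so training cannot confound them. Their power is low because the groups are small: it is about 56% even at 13:12. In addition, the 7.5-point difference is an assumption that runs against hypothesis 1 in section 1, which expects the trainings to be equally effective.

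Finally, sub-study 2 enrolment is scheduled from July 2022 and the SAP is dated November 2022, so new lists may arrive after allocation has begun. That is a fair cost. It does not affect the model term.

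**Conclusion.** The point holds as a defect in the stated rule with a modest statistical consequence. The equal four-way split contradicts the fixed training arm, and the SAP leaves open both whether the injection draw is balanced within training arm and whether the pooled model accounts for training.

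With one list, 50 entrants and 25 per training arm, a 15:10 or worse split has probability about 26%. The 25/25 exit split is assumed, since the SAP gives no figure per arm. The consequence is a standard error about 4% larger for the pooled contrast if the trainings differ by 7.5 points, and 2 to 3 percentage points less power for a within-training comparison at 15:10 or 16:9. Both results use SD 13 carried over from sub-study 1. The 22 per pooled group stands. The change is worth making because it costs very little, not because the primary conclusion is in danger.

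**What to change.** 1. In section 3, Sub-study 2, replace the equal division into four groups with a statement that patients are randomised 1:1 to HVI or CS in permuted blocks of 2 and 4, and that the four groups result from this draw and the training already allocated.
2. In sections 5 and 7.2, name sub-study 1 training arm as a factor in the sub-study 2 model for 3+5 v 4+6, for all patients. Section 7.4 says that no analysis had started when the SAP was signed, so this term can be specified without knowledge of results.
3. For patients not yet randomised, keep one list for HSR and one for app training, and say so in place of the sentence on stratification. If separate lists are already in use, a sentence stating this is enough.

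The cost is a few sentences, one model term and a second list. Patients already allocated stay on the existing list, so the allocation scheme would be mixed and the report should say so. Two lists can also leave the overall HVI:CS difference slightly larger: at most 4 in the simulations, against 2 with one list.
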